Outcome measures: The primary outcome will be neurological disability at hospital discharge assessed with the Modified Rankin Scale (mRS),^{48,49} a well-validated and widely used outcome measures in stroke clinical trials. The scale runs from 0-6, from perfect health without symptoms to death (**Table 4**). All raters will be trained and certified in mRS assessment⁵⁰ and will use a structured questionnaire and interview, which have been shown to produce very good interobserver reliability.^{51,52} We will measure the Full Outline of UnResponsiveness (FOUR) Score^{53,54} at 72 hours post-ROSC (**Table 5**). The FOUR Score consists of four components with a maximum score of four for each component and allows for assessing intubated patients and brainstem reflexes. We will also perform neuropsychological testing at 180 days after resuscitation for all patients who survived to hospital discharge. We will use an NHLBI-sponsored methodology for performing centralized, telephone-based cognitive testing, which has been previously validated for use in multi-center clinical studies.⁵⁵⁻⁶⁰

Neuropsychological testing will use validated instruments across five cognitive domains: (1) attention, Wechsler Adult Intelligence Scale-IV-digit span; (2) reasoning, Wechsler Adult Intelligence Scale-IV-similarities; (3) immediate and delayed memory, Wechsler Memory Scale-III-logical memory I and II; (4) verbal fluency, Controlled Oral Word Association Test; and (5) executive functioning, Hayling Sentence Completion Test. We will also assess

Table 4: Modified Rankin Scale

Scale	Description
0	No symptoms.
1	No significant disability. Able to carry out all usual activities, despite some symptoms.
2	Slight disability. Able to look after own affairs unassisted, but unable to carry out all previous activities.
3	Moderate disability. Requires some help, but able to walk unassisted.
4	Moderately severe disability. Unable to walk and attend to own bodily needs unassisted.
5	Severe disability. Requires constant nursing care and attention, bedridden, incontinent.

Table 5: Full Outline of UnResponsiveness Score

Component	Scoring
Eye Response	4 = eyelids open or opened, tracking, or blinking to command 3 = eyelids open but not tracking 2 = eyelids closed but open to loud voice 1 = eyelids closed but open to pain 0 = eyelids remain closed with pain
Motor Response	4 = thumbs-up, fist, or peace sign 3 = localizing to pain 2 = flexion response to pain 1 = extension response to pain 0 = no response to pain or generalized myoclonus status
Brainstem Reflexes	4 = pupil and corneal reflexes present 3 = one pupil wide and fixed 2 = pupil or corneal reflexes absent 1 = pupil and corneal reflexes absent 0 = absent pupil, corneal, and cough reflex
Respiration	4 = not intubated, regular breathing pattern 3 = not intubated, Cheyne-Stokes breathing pattern 2 = not intubated, irregular breathing 1 = breathes above ventilator rate 0 = breathes at ventilator rate or apnea

orientation and judgment using the COGNISTAT- Neurobehavioral Cognitive Status Exam (NCSE). Functional outcome assessment will use validated measures of ability to return to work. The telephone-based cognitive battery allows for uniformity in cognitive assessment for patients enrolled across all study sites. Subjects who complete the telephone-based cognitive battery will be compensated \$100 for their time. Other measures: Post-ROSC hyperoxia may also have extracerebral effects. We will calculate the extracerebral Sequential Organ Failure Assessment (SOFA) score,⁶¹ which quantifies respiratory, cardiovascular, renal, hepatic, and coagulation system failure for 0-6 hours and 6-36 hours. We have experience using SOFA as an outcome measure to quantify organ failure.⁶¹⁻⁶⁴ These data will permit secondary analyses of the association between hyperoxia exposure and non-neurologic organ failure (i.e. total SOFA minus the neurological component⁶¹).

Analysis

We will begin the analysis with descriptive statistics for the entire cohort. We will report categorical data as proportions with 95% confidence intervals and continuous data as means with standard deviations or medians with interquartile ranges as appropriate. Using the data collected for PaO₂ and SaO₂ over time as described above, we will compute the time-weighted average (TWA) PaO₂ and SaO₂ over the first 24 hours after ROSC. Computing TWA is a common method for quantifying exposures over time in epidemiological research,⁶⁵⁻⁶⁷ including studies of exposures and subsequent cognitive function.⁶⁸ The equations are:

$$\text{TWA-PaO}_2 = [(PaO_{2a} * \text{Time a}) + (PaO_{2b} * \text{Time b}) + \dots (PaO_{2z} * \text{Time z})] / (\text{Time a} + \text{Time b} + \dots \text{Time z})$$

$$\text{TWA-SaO}_2 = [(SaO_{2a} * \text{Time a}) + (SaO_{2b} * \text{Time b}) + \dots (SaO_{2z} * \text{Time z})] / (\text{Time a} + \text{Time b} + \dots \text{Time z})$$

We will build a multivariable regression model to test the association between TWA-PaO₂ and mRS at hospital discharge, adjusting for covariates previously demonstrated to be associated with poor neurological outcome after cardiac arrest. Covariates to be considered include: (1) pre-arrest comorbidities (Charlson index⁶⁹), (2) prolonged downtime (downtime > 20 minutes) (yes/no), (3) initial arrest rhythm (pulseless electrical activity/asystole vs. ventricular tachycardia/ventricular fibrillation), and (4) arrest location (in-hospital vs. out-of-hospital).⁷⁰⁻⁷⁵ In addition, in order to account for patients with lung injury (i.e. inability to maintain adequate oxygenation) we will add PaO₂/FiO₂ < 100mmHg (yes/no) to the regression model. We will build separate models to test the association between TWA-PaO₂ (adjusting for the five covariates above) and each of the five cognitive domains in our neuropsychological testing. We will then repeat these analyses using TWA-SaO₂ as the exposure variable of interest. This approach will not only allow us to test for an independent association between the exposure and neurological disability and neuropsychological deficits, but will also allow us to pinpoint one or more types of cognitive deficit (e.g. attention, executive function) most closely associated with the exposure. Given outcome measures that are quantitative (i.e. z-score for each cognitive domain) or semi-quantitative (i.e. mRS at hospital discharge), we will treat these outcomes as *continuous* dependent variables for modeling. Using continuous measures of the exposure and outcomes (rather than collapsing the data into categorical variables) will permit detection of subtle effects that could be missed if only categorical analyses were employed.

Secondary analyses: We will compare proportions of good neurological outcome [defined as a mRS ≤ 3 (based on the preliminary data of our collaborator, [name], University of Pittsburgh)],⁴⁵ between subjects who receive the study intervention (i.e. rapid FiO₂ optimization) vs. those who do not receive the study intervention, using binomial test. Among survivors, we will compare the 180-day neuropsychological measures (composite z-scores for each cognitive domain) between the same two groups using t-test or Mann-Whitney U as appropriate with corrections for multiple comparisons. We will compare the proportions of patients able to return to work between the two groups using binomial test. We will compare plasma IsoPs/IsoFs at each time point between the two groups using t-test or Mann-Whitney U as appropriate with corrections for multiple comparisons.

Sample Size: The sample size calculation in the initial study proposal was based on the primary outcome, mRS at hospital discharge, and we planned to enroll a total of 266 subjects. To ensure adequate power to test the relationships between the above independent variables and cognitive domains, we assumed a medium relationship strength between the six independent variables and each of the five cognitive domains ($R^2 = 0.15$). In order to achieve 80% power and an $\alpha = 0.05$ we would require a minimal of 85 subjects to undergo neuropsychological testing at 180 days. This sample size will be among the largest prospective studies of

neuropsychological outcomes that we are aware of in the literature.^{8,29-32} Assuming a 15% drop out rate for lost to follow up for neuropsychological testing at 180 days we would require 98 subjects to be discharged with a mRS \leq 4. Based on preliminary data from REOX I we expect 35% of patients will be discharged with a mRS \leq 4 and undergo cognitive testing at 180 days. We would therefore require a minimal total sample size of 280 subjects between REOX I and II combined for the multivariable testing. We have enrolled 200 subjects in REOX I to date. We anticipate additional subjects to be enrolled in REOX I and therefore plan for 75 subjects to be enrolled in REOX II to ensure a total sample size of at least 280 subjects.

Overview of the safety monitoring plan and serious adverse event tracking: In order to help ensure adequate protection of human subjects enrolled in this clinical study, we established an independent three-member **Data Safety Monitoring Board (DSMB)** (see **DSMB Charter**). The Chair of the DSMB will be [name]. [name] is an established investigator and is currently the Director of Clinical Research, Department of Emergency Medicine, Cooper University Hospital, Camden, NJ. The DSMB will be charged with reviewing all serious adverse event reports and will also perform interim analysis of the data after one-third (n=25) and two-thirds (n=50) of the patients have been enrolled in REOX II. Given neither REOX I nor REOX II are blinded, all data reviewed by the DSMB will be unmasked. At both interim analyses the committee will be asked to render a decision as to whether the trial should be continued, modified, or stopped based on the safety profile of the interim data. We have defined the following *a priori* as a reportable serious adverse event (SAE): (1) any events resulting in death or repeat cardiac arrest; (2) sustained hypoxia (defined as $\text{SaO}_2 < 88\%$ for more than three consecutive minutes); (3) heart rate < 50 for greater than one minute; (4) documented cyanosis at any time; or (5) withdrawal of a subject from the trial for any reason. We will define excessive rates of any single SAE *a priori* as a $>15\%$ difference in the prevalence (% of total number in each group) between the two groups [i.e. subjects who receive the study intervention (i.e. rapid FiO_2 optimization) vs. those who do not receive the study intervention] at either interim analysis. A clinician can withdraw a subject from the study for worsening clinical status including worsening respiratory status (based on clinical judgment, arterial blood gas analysis, or increasing FiO_2 requirement). The site PIs at each collaborating institution will be responsible for reporting all predefined SAEs, as well as any other adverse events felt to be related to the study protocol, to the coordinating site, Cooper University Hospital. In addition to reporting all adverse events to the DSMB, all adverse events will be submitted to each institution's IRB for review.

Registration: This study will be registered on clinicaltrials.gov

References

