Our sites also have extensive experience implementing aggressive clinical treatment protocols for critically ill patients in the ED setting, and analyzing the effects using a before-and-after study design. Specifically, we have effectively implemented protocols for post-cardiac arrest care and hemodynamic optimization for sepsis.³⁷⁻⁴² Importantly, we also have experience continuing these aggressive treatment protocols into the ICU. Compared to our previous treatment protocols, which required the introduction of invasive hemodynamic monitoring or other complex procedures in the ED setting, our protocol for rapid FiO₂ optimization after resuscitation from cardiac arrest is relatively **straight-forward and quite feasible**. Our sites' clinical rationale for implementing the protocol in this application is that rapid FiO₂ optimization is now recommended in the American Heart Association (AHA) Guidelines for Cardiopulmonary Resuscitation and Emergency Cardiovascular Care⁴³ (and is now included in Advanced Cardiac Life Support [ACLS]) and a consensus statement on post-resuscitation care from the International Liaison Committee on Resuscitation (ILCOR).⁹ Therefore, the implementation of a rapid FiO₂ optimization protocol after resuscitation from cardiac arrest will be consistent with current consensus treatment guidelines, but at the same time will generate the most valuable clinical data to date regarding this fundamental element of post-cardiac arrest care.

C.3. Preliminary studies from the research team proposed in this application

C.3.1. Arterial hyperoxia after resuscitation from cardiac arrest is associated with poor outcome.

[figure not shown]
Kilgannon JH, Jones AE, Shapiro NI, Angelos MG, Milcarek B, Hunter K, Parrillo JE, Trzeciak S.

Association between arterial hyperoxia following resuscitation from cardiac arrest and in-hospital mortality.
JAMA 2010; 303(21):2165-71.

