- *Reduced neurological disability at hospital discharge (Aim 2)*
- *Reduced neuropsychological and functional deficits among survivors at 180 days (Aim 3)*

D.1.2. Overview

Design: Prospective protocol implementation study with an observational comparison group [REOX II (intervention component) versus REOX I (observational component)]

Participants: Adult patients resuscitated from cardiac arrest

Enrollment location: Emergency Departments of 6 urban academic medical centers

Intervention: Implementation of a clinical protocol for rapid FiO₂ optimization after ROSC from cardiac arrest.

Primary outcome: Good neurological outcome (defined as Modified Rankin Scale ≤ 3 ⁴⁵ at hospital discharge).

Secondary outcomes: Neuropsychological tests and ability to return to work among survivors at 180 days.

Mechanistic outcomes: Oxidative stress markers (IsoPs/IsoFs) in plasma 0-6 hours after ROSC.

Estimated sample size and study duration: 280 patients (205 from REOX I and 75 from REOX II).

[figure not shown]
D.2. REOX II Study Protocol

Study setting and population: This study is the second phase in a two-phase study. The initial phase, REOX I, was an observational-only study. As in REOX I, REOX II will identify subjects with return of spontaneous circulation (ROSC) after cardiac arrest in 6 hospitals (Cooper University Hospital, Camden, NJ; Hospital of the University of Pennsylvania and Penn-Presbyterian Medical Center, both in Philadelphia, PA; University of Mississippi Medical Center, Jackson, MS; Methodist Hospital, Indianapolis, IN; and Beth Israel Deaconess Medical Center, Boston, MA). The inclusion criteria are: age > 17 years; cardiac arrest; ROSC achieved; comatose (Glasgow Coma Scale motor score < 6) after ROSC; and clinician intent to treat with target temperature management. The exclusion criteria are: presumed etiology of arrest is trauma, hemorrhage or sepsis; resident of a nursing home or other long-term care facility; known or clinically apparent pregnancy; known lack of commitment to aggressive support by next of kin; and any other condition, that, in the opinion of the investigator, would preclude the subject from being a suitable candidate (e.g. end stage chronic illness with no reasonable expectation of survival to hospital discharge).

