Therapeutic interventions: **Table 3** displays the standard elements of post-resuscitation care across all centers. All sites are experienced in target temperature management after ROSC and target 32-36°C for 24 hours using external cooling devices (Arctic Sun, Medivance, USA, or Gaymar III, Gaymar Industries, USA). Using a standardized order set for target temperature management induction, we demonstrated successful achievement of target temperature in 96% of patients and a median time from ROSC to target temperature of four hours (i.e. faster than the landmark randomized trial) in our routine clinical care.⁴⁰ All standard elements in **Table 3** reflect current AHA recommendations.¹² All subjects in this study will receive standard post-resuscitation care. Since none of the sites previously had a protocol in place for FiO₂ titration after ROSC and our standardized order sets for post-resuscitation care do not have orders for FiO₂ titration, subjects in REOX I (observational only component) had clinician-directed FiO₂ titration after ROSC.

For the interventional component of this study we will implement the protocol for rapid FiO₂ optimization after cardiac arrest (**Figure 10**) at all sites. Once a subject is identified and written informed consent is obtained from a surrogate, the study intervention (i.e. rapid FiO₂ optimization protocol) will be activated by the investigator who receives notification in real-time. (see “*Patient identification and recruitment*” above). The on call investigator will communicate directly with the clinical care team at the bedside and will ensure activation and adherence to the clinical protocol. Subjects enrolled in the study intervention will receive standard post-resuscitation care in **Table 3** *plus* rapid FiO₂ optimization according to **Figure 10**. Our sites have an outstanding track record of sustained clinical adherence to new resuscitation protocols for multi-year time periods.³⁷⁻⁴² Subjects who are excluded from the study intervention due to lack of informed consent within the first four hours after ROSC, will still be eligible for the observational only aspect of this study (REOX I). These subjects will receive standard post-resuscitation care outlined in **Table 3**, but will not have activation of the rapid FiO₂ optimization.

Table 3: Standard elements of post-cardiac arrest care across all centers. (TH = therapeutic hypothermia; GCS = Glasgow Coma Scale; ROSC = return of spontaneous circulation)

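### Nearly all comparison patients come from the earlier phase and no planned analysis uses enrolment date, so drift in care between phases can pass as a protocol effect and, more weakly, as a PaO2 effect

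*Combined protocol and SAP*

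**What the plan says.** The Design line in D.1.2 describes a "Prospective protocol implementation study with an observational comparison group [REOX II (intervention component) versus REOX I (observational component")]. D.2 (Study setting and population) puts the phases in sequence: "This study is the second phase in a two-phase study. The initial phase, REOX I, was an observational-only study". D.1.2 plans "280 patients (205 from REOX I and 75 from REOX II" patients, and the Sample Size paragraph states "We have enrolled 200 subjects in REOX I to date".

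REOX I does not close when REOX II opens. Under Therapeutic interventions, patients who miss the intervention because no surrogate consented within four hours of ROSC "will still be eligible for the observational only aspect of this study (REOX I"). They receive clinician-directed FiO2 titration.

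The Analysis section regresses mRS at discharge, and each of five cognitive domains, on TWA-PaO2 and then on TWA-SaO2. The covariates are Charlson index, downtime above 20 minutes, initial rhythm, arrest location and PaO2/FiO2 below 100 mmHg. Secondary analyses compare patients who did and did not receive the intervention. They use a binomial test for mRS ≤3 and for return to work, and a t-test or Mann-Whitney U for the cognitive scores and the plasma markers. Neither enrolment date nor study phase is a covariate, and no trend analysis or restriction to recent or concurrent controls is planned.

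On oxygen practice, C.2 says that rapid FiO2 optimization "is now recommended in the American Heart Association (AHA) Guidelines for Cardiopulmonary Resuscitation and Emergency Cardiovascular Care" and has entered ACLS.

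**The concern.** With an almost wholly earlier control group, treatment group and calendar period nearly coincide. Adjusting for case-mix does not remove a change in care over time, and the group tests adjust for nothing. If outcomes improved for other reasons, the improvement would be credited to the protocol. If PaO2 also fell over the same years, date would be a common cause of lower PaO2 and better outcome, and the pooled PaO2 slope would move towards apparent harm from oxygen.

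The stake is Aim 2. D.1.2 names mRS ≤3 at discharge as the primary outcome. The only planned comparison of that outcome between patients with and without the protocol is the unadjusted binomial test, which cannot separate protocol from period.

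**Working it through.** **Inputs from the plan.** 205 v 75 patients (D.1.2). 200 REOX I patients already enrolled, so 205 − 200 = 5 planned patients remain (Sample Size). Five covariates plus the exposure make six independent variables; R² = 0.15, 80% power, α = 0.05, 85 tested, 15% dropout, 35% discharged with mRS ≤4 and tested (Analysis; Sample Size).

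**Assumptions, because the documents give no figures.** 30% good outcome; drift of 2 to 8 percentage points between the phases; even accrual; for the simulation, mRS SD 2 and the PaO2 values below.

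**The plan's own figure.** Overall F test with f² = 0.15/0.85 = 0.176, noncentrality N·f² and six variables: power first reaches 80% at N = 84 and is 0.808 at the stated 85. Then 85 × 1.15 = 97.75, or 98, and 98/0.35 = 280. The stated figures reproduce, so this point does not rest on an arithmetic error.

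**Group comparison of mRS ≤3, no protocol effect.**

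SE = √[0.3 × 0.7 × (1/75 + 1/205)] = 0.0618

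Error = P(Z > 1.96 − b/SE) + P(Z < −1.96 − b/SE), where b is the drift between phases.

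| Drift b | b/SE | Actual two-sided error |
|---|---|---|
| 2 points | 0.32 | 0.051 + 0.011 = 6% |
| 4 points | 0.65 | 0.095 + 0.005 = 10% |
| 6 points | 0.97 | 0.161 + 0.002 = 16% |
| 8 points | 1.29 | 0.253 + 0.001 = 25% |

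If the five remaining controls are concurrent and share the later period, b shrinks by 200/205 = 0.976. The last row then becomes 24%, and the others move by less than one point.

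**Pooled PaO2 model.** I used a simulation with 1,500 runs per setting, no causal effect of PaO2 or of the protocol, and mRS drifting linearly over the study. PaO2 started at 170 mmHg (SD 70), fell by 0, 40 or 80 mmHg over the study and dropped a further 40 mmHg under the protocol. No other covariates were simulated.

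| mRS drift over whole study | Phase contrast rejects | PaO2 coefficient rejects |
|---|---|---|
| 0.5 point | 13–16% | 6–10% |
| 1.0 point | 42–44% | 7–17% |

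With date in the model, both return to about 4–6%. That recovery relies on the fitted (linear) form of the trend being right. A step change in care at the phase boundary could not be separated from the protocol.

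**Price of adjusting.** With seven variables and the same total R², power at 85 tested falls from 0.808 to 0.778, and 80% needs 89 tested. That means 89 × 1.15/0.35 = 292.4, or 293 patients, by the plan's own steps. Dividing by 0.85 instead gives 105 discharged and 105/0.35 = 300.

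For the group contrast, even accrual with five concurrent controls gives a phase–date correlation of 0.747 and variance inflation 1/(1 − 0.747²) = 2.26. A difference of 30% v 48.2% has 80% power unadjusted. Its unpooled SE is √(0.3 × 0.7/205 + 0.482 × 0.518/75) = 0.0660. Multiplied by √2.26 this is 0.0992, so power is Φ(0.182/0.0992 − 1.96) = Φ(−0.125) = 45%. With 20 or 40 concurrent controls it is about 53% or 60%.

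**The case against.** **No drift is documented.** This stands. The oxygen recommendation in C.2 is cited to publications of 2008 and 2010 in the reference list, and no REOX I enrolment dates are given. It may have applied equally to both phases. No site had an FiO2 titration protocol before, and REOX I titration was left to clinicians. Falling background PaO2 is plausible, not shown.

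**A reader might infer that temperature practice was also changing**, because sites "target 32-36°C for 24 hours using external cooling devices". The documents do not support that. They give one range and one list of standard care for all subjects (Table 3) and describe no change over time. A wide range is not a trend.

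**Concurrent controls exist, and their number is not capped.** Sample Size expects further REOX I patients and a total of at least 280. This softens the problem but does not remove it, because these patients are selected by lack of timely surrogate consent.

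**The plan claims only association, and the Analysis section lists the exposed test as secondary.** Both are true. Yet the aims concern the protocol, and this test is the only one that compares mRS ≤3 by protocol.

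**Covariates are only to be considered, so date could be added later.** The Analysis section then refers to a fixed five, and the sample size counts six independent variables including the exposure. Neither count leaves room for date.

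**Date adjustment costs too much.** For the group contrast the loss is large, and the adjusted estimate is mostly an extrapolation of the REOX I trend. This is a sound argument against making it decisive, but not against reporting it.

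**Conclusion.** The point holds as a limitation of the analysis plan. About 200 of 205 planned comparison patients precede REOX II, and no planned analysis uses date or phase to separate period from protocol. Under the assumptions stated (30% good outcome, 205 v 75, no protocol effect), drift of 2 to 8 points lifts the two-sided 5% error of the group comparison to about 6% to 25%.

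Two stronger readings go too far. One is that the TWA-PaO2 models are equally threatened: in the simulation they are less exposed, at 6–17% against 13–44% for the phase contrast. The other is that a protocol effect should be claimed only if it survives date adjustment: at about 45% power, that rule would often discard a real effect. The size of any actual drift is unknown, so this is a cheap improvement to the plan and not evidence that its results will be wrong.

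**What to change.** 1. Add enrolment date (linear, or a restricted cubic spline) to the pooled TWA-PaO2 and TWA-SaO2 models, and report results with and without it.
2. For REOX II v REOX I, pre-specify two sensitivity analyses: a date-adjusted contrast, and one limited to the most recent REOX I patients, with the window fixed before outcomes are compared. Report the number of concurrent REOX I patients and how they came to be there.
3. If these disagree with the unadjusted result, word the conclusion as an association that cannot be separated from period.

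No new patients or procedures are needed, and enrolment dates should be available from prospectively collected data. The cost is precision. Overall F-test power at 85 tested falls from about 0.81 to 0.78, assuming that date adds nothing to R². The date term also absorbs part of the PaO2 contrast that the protocol creates, because that contrast falls in the later period; hence reporting both versions. The date-adjusted group contrast carries a variance inflation of about 2.3 under even accrual with five concurrent controls, so it belongs among the sensitivity analyses.
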